### Methods: Data collection, management, and analysis

Data collection	RT-PCR result is reported with cycle of quantification Cq for positive tests together
methods	with the Cq for human DNA in the sample.
	Antigen tests are reported according to the manufactor's instruction and divided
	into positive, negative, inconclusive or invalid tests. Inconclusive and invalid tests

	are handled according to the manufactor's instruction. Each antigen test is
	photographed to document the result.
	In the retrospective study arm all antigen tests are tested with stored excess
	material with seeking 50 samples with Cq 20 to 25, 50 samples with Cq 25 to 30, 50
	samples with Cq 30-35 and 50 samples with Cq >35. The 100 negative samples are
	pooled negative samples that are retested by RT-PCR again prior to use.
Data	Written consent for participation and collection of data in the study will be collected
management	at the test center and each consent is marked with the local sample identifier
	number. For consecutive samples each antigen test and the sample for RT-PCR at
	the DTU test center will be marked with the local sample identifier number and data
	will be paired according to this sample identification number. Individuals positive for
	SARS-CoV-2 will be invited in person, by phone or electronically for additional
	testing and individuals who agrees to additional testing, except in-patients will be
	contacted using their self-reported contact information's. The number of individuals
	contacted and rejecting participation will be registered, without additional
	information. At each retest a new sample identifier number will be pair with the
	swab(s) for RT-PCR testing at the DTU test center and the antigen tests conducted
	bedside by trained hospital personnel or outpatient team. Data including photo
	documentation of antigen test results will be send to the steering group and stored
	in a secure regional file archive.
Statistical	Prospective arm: Performance of each antigen test will be reported as sensitivity,
methods	specificity, positive predictive value (PPV) and negative predictive value (NPV)
	compared to oropharyngeal swabs evaluated by RT-PCR. Clinical performance of
	antigen tests will be further evaluated in respect to strong (Cq <25), intermediate
	(Cq 25-35) and weak (Cq >35) RT-PCR tests and in respect to samples with low SARS-
	CoV-2 RNA to human DNA ratio, equal SARS-CoV-2 RNA to human DNA ratio and
	high SARS-CoV-2 RNA to human DNA ratio.
	Among consecutive collected prospective samples the fraction of samples negative
	for human DNA by RT-PCR will be reported.
	Retrospective study arm: Determination of analytical sensitivity, specificity stratified
	into four groups by PCR (Cq 20-25, Cq 25-30, Cq 30-35 and Cq >35).
	Comparison of sensitivity and specificity between antigen test will be done using
	McNemar chi-squared test. Comparison of PPV and NPPV between antigen test will
	be done by bootstrap test.
	95 % Confidence intervals for sensitivity, specificity, positive predictive value and
	negative predictive value are calculated as bootstrap confidence intervals.

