	gene) of SARS-CoV-2 and for the RNase P gene (RP-gene) from humans to as process
	control and confirmation of the presence of human DNA in the sample.
	Excess material from negative patients will be discharged after testing. Excess
	material from previous positive patients will be discharged. Sample material from

	prospective positive individuals will be treated according to normal practice at the
	local DCM.
	For the retrospective study arm, stored excess material from 200 previously positive
	and 100 negative SARS-CoV-2 samples stored at -80 °C is defrosted on ice and
	checked by RT-PCR to ensure the Cq value. Selected samples are defrosted again on
	ice and aliquoted into 250 μL volume and stored at -80 °C until use. For each test
	one aliquot of each sample is defrosted and 200 µL sample in UTM is tested
	according to the manufacturer's instruction by laboratory trained personnel in
	collaboration between DCM Hvidovre, RH and SSI. One aliquot is used for each test
	and excess material is discharged. One aliquot is retested by RT-PCR after thawing to
	verify the Cq of the sample.
Outcomes	Primary outcome: Performance of each antigen in relation to the RT-PCR test result.
	Secondary outcomes: Performance of each antigen test in relation to the cycle of
	quantification Cq by RT-PCR with and without normalization towards human DNA.
	The fraction of consecutive samples negative for human DNA by RT-PCR.
	Agreement between oropharyngeal swabs and tests from other anatomical test
	locations by RT-PCR.
	Analytical sensitivity and specificity of each antigen test on retrospectively collected
	SARS-CoV-2 positive and negative samples. SARS-CoV-2 positive samples are
	stratified into subgroups according to Cq by RT-PCR.
Participant	Either included when referred to SARS-CoV-2 testing and agrees to participate in the
timeline	testing or being invited as in-patient, by phone or electronically and agrees to
	retesting after a positive SARS-CoV-2 RT-PCR test. Invited in- or out-patients positive
	for SARS-CoV-2 are retested with their consent again as soon as possible after first
	positive RT-PCR test by an outpatient screening team, who visits and samples each
	patient at home or for in-patients by trained hospital personnel.
Sample size	Prospective study arm. 200 SARS-CoV-2 RT-PCR positive and 200 SARS-CoV-2 RT-PCR
Sample size	negative patients included for each antigen test.
	Retrospective study arm. 200 SARS-CoV-2 RT-PCR positive and 100 SARS-CoV-2 RT-

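### Does describing the 100 retrospective negatives as pooled leave the analytical specificity undefined?

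*Protocol*

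**What the plan says.** The Protocol describes the retrospective negatives in three places.

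- **Interventions** (Methods: Participants, interventions, and outcomes). The material is introduced with "For the retrospective study arm, stored excess material from 200 previously positive" and "and 100 negative SARS-CoV-2 samples stored at -80 °C is defrosted on ice and" a check of the Cq value. Selected samples are then thawed again, split into 250 µL aliquots and refrozen. For each antigen test, "one aliquot of each sample is defrosted" and tested. Positives and negatives share this description, and no pooling step appears in it.
- **Sample size** (same section). The arm is counted as 200 RT-PCR-positive and 100 RT-PCR-negative samples per antigen test.
- **Data collection methods** (Methods: Data collection, management, and analysis). The positives are spread over four Cq bands of 50. The 100 negatives are "pooled negative samples that are retested by RT-PCR again prior to use".

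These negatives feed one secondary outcome: "Analytical sensitivity and specificity of each antigen test on retrospectively collected" positive and negative samples. Statistical methods adds McNemar tests for comparing antigen tests on sensitivity and specificity, and bootstrap 95% intervals. It does not name the resampling unit.

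**The concern.** Only the negatives are called pooled, and only in one of the places that describe them. A reader could conclude that the Protocol has two ideas of what the 100 specimens are. Two consequences would follow.

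1. **Meaning of the estimate.** The false-positive rate of a pool is not that of a single sample. Mixing can dilute one donor's interfering material below the level that triggers a false line, or it can carry that material into more test units. Sensitivity in the same arm rests on samples not described as pooled, so the two halves of the outcome would refer to different kinds of specimen.
2. **Precision.** If the 100 units were repeated aliquots of a few pools, results within a pool could be correlated. A bootstrap or McNemar test that counts 100 independent units would then claim too much information.

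At stake are the analytical specificity of each test and the between-test comparison of that specificity in this arm.

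**Working it through.** **No figure to reproduce.** The 100 negatives are a fixed number. The Protocol states no expected specificity, precision target, alpha or power for them, so no formula can return it.

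**Step 1: can the descriptions hold together?**

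| Place | What it fixes | What it leaves open |
|---|---|---|
| Interventions | stored excess material; 100 negatives; one aliquot of each per test | whether a negative comes from one donor or several |
| Sample size | 100 negative samples per test | the same |
| Data collection methods | the 100 negatives are pooled and rechecked by RT-PCR | number of pools, donors per pool |

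Interventions never says that a negative sample comes from one individual. If stored negative material is combined into 100 pools and each pool is aliquoted, every row is satisfied. All three places count 100, and one aliquot of each is used per test, so 100 distinct pools is the natural joint reading.

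**Step 2: precision on that reading.** With 100 independent units and no false positives, the exact upper 95% limit is 1 − 0.025^(1/100) = 3.6%. Pooling does not widen it. For the 200 prospective negatives, 1 − 0.025^(1/200) = 1.8%.

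**Step 3: what fewer pools would do.** The number of pools m and the within-pool correlation ρ are assumptions; the Protocol gives neither. The effective number is 100 / [1 + (100/m − 1)ρ], entered in the same limit.

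| m | ρ | Effective n | Upper limit at 0/100 |
|---|---|---|---|
| 100 | any | 100 | 3.6% |
| 50 | 0.2 | 100/1.2 = 83.3 | 4.3% |
| 50 | 1.0 | 50 | 7.1% |
| 20 | 0.2 | 100/1.8 = 55.6 | 6.4% |
| 20 | 1.0 | 20 | 16.8% |

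**Step 4: McNemar error.** This was simulated with 40,000 runs, both tests having a 5% false-positive rate and no continuity correction. With 100 independent units the error is about 4%. With 20 pools and ρ = 0.2 it depends on whether a pool's tendency to give false positives is shared by the two tests: about 13% if independent between tests, 9.2% if half shared, 4.3% if fully shared. Interfering material in a pool could well affect both tests, so the honest range is about 4% to 13%, and only if there are as few as 20 pools.

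**Step 5: pooled against individual rate.** For an individual false-positive rate p and k donors per pool, the pooled rate lies between 0 (complete dilution) and 1 − (1 − p)^k (no dilution). With p = 2% and k = 5 the upper end is 1 − 0.98^5 = 9.6%; with p = 1% and k = 5 it is 4.9%. Both p and k are assumed. The bounds show that the rates can differ, but not in which direction.

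**The case for a change.** The best case for a change is that the nature of the specimen is a laboratory design matter. This Protocol itself sets it, in two places, so an analysis plan would inherit the gap and could not cure it. Analytical sensitivity and specificity are reported side by side for each test, and a reader may take them as describing the same kind of material. A sentence giving the number of pools and the donors per pool would cost almost nothing.

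Part of this stands. The description is incomplete, and a report that gave the specificity without saying the negatives were pooled would be less informative than it should be. But the document already separates analytical from clinical performance in its Objectives, and the retrospective result is labelled analytical: a bench measurement on stored material. Nowhere does it claim that the figure carries over to individuals.

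Using 100 individual negatives instead would be a different laboratory choice, not the repair of an error. Each would have to supply 250 µL × (number of antigen tests + 1 RT-PCR aliquot), which is 1.25 mL for 4 tests and 2.25 mL for 8 (the number of tests is assumed). The positives face the same demand, but limited volume is a plausible reason to pool negatives, and no bias in a known direction has been shown that would outweigh it.

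**Conclusion.** The concern does not call for a change. The passages are compatible, and what is missing is detail. Read as 100 distinct pools, the plan gives a sound bench-level specificity on 100 units, with the interval width it appears to have (upper limit 3.6% at zero events). The wider limits of 4.3% to 16.8% and the McNemar error above about 4% arise only with fewer than 100 independent pools, which nothing in the text indicates. If the sample list did show repeated aliquots from the same pool, an analyst would ordinarily resample and compare by pool, and the choice of resampling unit is commonly left to an analysis plan.

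The reach is small in any case. It covers one secondary outcome and its between-test comparison. The primary outcome and the specificity from the 200 prospective RT-PCR-negative patients per test are unaffected. This conclusion rests on the natural joint reading of the count of 100. The Protocol does not state the number of pools outright, so that reading is an inference.

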# Methods: Participants, interventions, and outcomes

- · · · · · ·	
Study setting	Test centers screening out-patients and hospital staff for SARS-CoV-2 and
	hospitalized patients positive for SARS-CoV-2. Test centers are invited to participate nationwide.
	All RT-PCR tests are conducted at the DTU test center and all retrospectively testing
	of samples by antigen tests is conducted in collaboration between DCM Hvidovre,
	Rigshospitalet and SSI.
Eligibility criteria	Inclusion criteria. Age 18 years or over, has the capacity to give informed, written
	consent and be able to cooperate to the additional testing.
	Exclusion criteria. Individuals not fulfilling the inclusion criteria or declining
	additional pharyngeal swabbing or saliva swabs.
Interventions	200 consecutive individuals are tested for SARS-CoV-2 by RT-PCR and antigen test.
	When RT-PCR results are available, additional individuals who has tested positive for
	SARS-CoV-2 (within 24 hours of positive test result to contact) are invited to
	participate in the study. SARS-CoV-2 positive individuals are retested until 200 RT-
	PCR positive individuals and 200 RT-PCR negative individuals have been included for
	each antigen test.
	Testing is done with three oropharyngeal swabs at a time in a tree point swab
	procedure. The three swabs are held together and rotated at both tonsils and at the
	back of the oro-pharynx. Additional nasal swabs, saliva swabs or breath test will be
	collected for additional antigen and RT-PCR testing.
	The consecutive 200 individuals are tested locally by RT-PCR and the residual
	volume in NEST-buffer is sent to the DTU test center to ensure that all individuals
	are tested in the same RT-PCR setup. Saliva swabs are when relevant processes
	according to the manufactures procedure locally and the samples are sent to the
	DTU test center for RT-PCR. Additional oropharyngeal swabs, nasal swabs, saliva
	collection, self-test and breath tests are used for antigen testing according to the
	manufacturer's instructions locally at the test center. Positive patients that are
	retested, are tested at home / bed-side by an range of antigen tests and one
	oropharyngeal swab is sent to DTU test center for RT-PCR together with samples
	from other anatomical test locations when relevant. For self-test tested individuals
	will send a picture and their interpretation of the test to the test-coordinator.
	The DTU test center will test for two targets in the Nucleocapsid protein gene (N-

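### PPV and NPV are taken from a sample fixed at 200 RT-PCR positives and 200 negatives, so they describe an artificial 50% prevalence and not the people being screened

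*Protocol*

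**What the plan says.** The case mix is set in the protocol under *Methods: Participants, interventions, and outcomes*. The Interventions row starts with a screening sample: "200 consecutive individuals are tested for SARS-CoV-2 by RT-PCR and antigen test". It then enriches: "When RT-PCR results are available, additional individuals who has tested positive for" the virus are invited, and retesting goes on until 200 RT-"PCR positive individuals and 200 RT-PCR negative individuals have been included for" each antigen test. The Sample size row repeats the quota: "Prospective study arm. 200 SARS-CoV-2 RT-PCR positive and 200 SARS-CoV-2 RT-PCR" "negative patients included for each antigen test".

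The setting is described as "Test centers screening out-patients and hospital staff for SARS-CoV-2 and" hospitalised patients who are positive.

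Under *Methods: Data collection, management, and analysis*, the Statistical methods row reports the prospective arm as sensitivity, "specificity, positive predictive value (PPV) and negative predictive value (NPV"), against RT-PCR on oropharyngeal swabs. It plans a comparison between tests ("McNemar chi-squared test. Comparison of PPV and NPPV between antigen test will" use a bootstrap test) and bootstrap 95% intervals for all four measures. The same row limits one result, the fraction of samples without human DNA, to consecutively collected samples. It puts no such limit on PPV or NPV, and mentions neither re-weighting nor a reference prevalence.

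**The concern.** Sensitivity and specificity are computed within RT-PCR positives and within RT-PCR negatives, so a quota on the two groups does not by itself distort them. PPV and NPV are computed across the two groups and depend directly on the ratio between them. Here that ratio is chosen by the investigators.

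The Outcomes row makes performance against RT-PCR the primary outcome, and the Statistical methods define performance by these four measures. PPV and NPV are therefore part of the primary result. The background asks for accuracy in real-life use, and the ethics section says the results should clarify whether the tests can serve rapid diagnosis in the health-care system. A reader will take the published PPV as the chance that a positive result at a test centre is true. A test whose positives are mostly false in low-prevalence screening could be published with a PPV near 99%. The NPV would make the same test look much worse at ruling out infection than it is in that setting.

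**Working it through.** **Inputs from the protocol.** 200 RT-PCR positives and 200 RT-PCR negatives per antigen test; 200 consecutive individuals; top-up by recruiting known positives only. The protocol states no expected sensitivity, specificity, prevalence, power or precision target, so the 200 + 200 cannot be re-derived. The values of Se, Sp and p below are assumptions.

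**Step 1: prevalence built into the arm.** 200/(200 + 200) = 50%.

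**Step 2: what the design implies about real prevalence.** Among 200 consecutive people at prevalence p, 200p positives are expected. For p = 1% to 10% that is 2 to 20, leaving 198 to 180 of the 200 positives to come from enrichment. Only positives are topped up, so the 200 negatives must come almost wholly from the 200 consecutive people, apart from retested people who have turned negative. The quota fits a consecutive sample that is nearly all negative, which is far from 50%.

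**Step 3: formulas.**

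- PPV = Se·p / [Se·p + (1 − Sp)(1 − p)]
- NPV = Sp(1 − p) / [Sp(1 − p) + (1 − Se)p]

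For example, with Se 0.70, Sp 0.99 and p = 0.01: PPV = 0.0070/(0.0070 + 0.0099) = 41.4%, and NPV = 0.9801/(0.9801 + 0.0030) = 99.7%.

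| Prevalence | PPV | NPV |
|---|---|---|
| 50% (as designed) | 98.6% | 76.7% |
| 10% | 88.6% | 96.7% |
| 5% | 78.7% | 98.4% |
| 2% | 58.8% | 99.4% |
| 1% | 41.4% | 99.7% |
| 0.5% | 26.0% | 99.8% |

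Under these assumptions most positives are false once 0.70p < 0.01(1 − p), that is, p < 0.01/0.71 = 1.4%.

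**Step 4: other accuracies.**

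- Sp 0.99, Se 0.50 to 0.90: PPV is 98.0% to 98.9% at 50%, but 33.6% to 47.6% at 1%. NPV is 66.4% to 90.8% at 50%, but 99.5% to 99.9% at 1%.
- Se 0.70, Sp 0.97 to 0.995: PPV is 95.9% to 99.3% at 50%, but 19.1% to 58.6% at 1%.

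**Step 5: the bootstrap does not help.** Se 0.70 and Sp 0.99 in 200 + 200 correspond to 140 true positives, 60 false negatives, 198 true negatives and 2 false positives. Resampling these 400 gives a 95% interval for PPV of 96.3% to 100%. That excludes the 41.4% that applies at 1%, because each resample keeps roughly the same artificial mix. When simulated sensitivity and specificity (200 per group) are put through the PPV formula at p = 1%, the interval is 21.6% to 100%; at 5% it is 58.9% to 100%.

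**Step 6: comparison between tests.**

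- Same mix, different accuracy: with Se 0.70, specificities of 99% and 98% give PPV 98.6% and 97.2% at 50%, a gap of 1.4 points. At 1% they give 41.4% and 26.1%, a gap of 15.3 points.
- Same accuracy, different achieved counts: with Se 0.70 and Sp 0.98, 200:200 gives NPV 196/(196 + 60) = 76.6%, and 200:150 gives 147/(147 + 60) = 71.0%.

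**The case against.** The strongest reply has four parts.

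- **Pooling is inferred.** The protocol assigns PPV and NPV to the prospective arm without saying in so many words that all 400 people are pooled, and an analysis plan not at hand might restrict them. But the pooled reading is the natural one. The authors did limit another result to consecutive samples and did not do so here. The protocol fixes the reporting; it does not leave it open.
- **The objectives name only sensitivity and specificity.** This is true, and with both published a reader could derive predictive values at any prevalence. No data are lost. It does not make the published PPV and NPV right for the setting.
- **The size is assumed.** Recruitment is of people with suspected infection referred for testing, and hospitalised positives belong to the setting, so prevalence may exceed 1%. At 10% the PPV is 88.6%, not 41.4%. This stands: the direction is certain below 50%, and the size depends on a prevalence that the protocol does not give.
- **The between-test comparison is less damaged.** When two tests share one case mix, the ranking of their PPVs follows the positive likelihood ratio and that of their NPVs the negative likelihood ratio, whatever the prevalence. A test of equality therefore remains meaningful. This also stands. What goes wrong is the size of the reported difference, and the ranking as well if achieved mixes differ. The 200:150 case would need a shortfall or unequal invalid results, so it is a secondary point.

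**Conclusion.** The concern holds and should be corrected before analysis. As written, the protocol reports, puts intervals on and compares predictive values at a prevalence of 50% that results from quota recruitment, without saying so. PPV will be overstated and NPV understated for any screening prevalence below 50%, and the design itself points to one far below that. Assuming 70% sensitivity and 99% specificity, PPV is overstated by 10.0 points at 10% prevalence (98.6 − 88.6), 19.9 at 5% (98.6 − 78.7) and 57.2 at 1% (98.6 − 41.4). NPV is understated by 20.0, 21.7 and 23.0 points at the same prevalences. The achieved mix may drift from exactly 1:1, for example when retested people have turned negative, but it would still be set by recruitment. The quota does not in itself invalidate sensitivity and specificity.

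**What to change.** Amend the Statistical methods as follows.

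- Do not compute PPV and NPV from the pooled 200 + 200 sample. Derive them by Bayes' rule from the estimated sensitivity and specificity at stated prevalences: the prevalence observed among the consecutive individuals, and a fixed grid such as 0.5%, 1%, 5% and 10%.
- Build the intervals by carrying the uncertainty of sensitivity and specificity through the formula. Where the consecutive-sample prevalence is used, carry its uncertainty too, since it may rest on only some 2 to 20 positives.
- Drop the bootstrap comparison of PPV and NPV on the enriched sample, or run it at one common stated prevalence for all tests.
- Print the reference prevalence beside every PPV and NPV.

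The cost is wording and a few lines of analysis, with no extra participants. PPV will look less favourable and its interval will be much wider at low prevalence, because 200 negatives give only a rough estimate of the false-positive rate. That width is real uncertainty which the pooled figure conceals.

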#### Introduction

# Background and rationale

Multiple antigen tests targeting SARS-CoV-2 are being marketed commercially, accompanied by reporting of accuracy by the vendor. To evaluate the real-life accuracy of such tests, independent user-initiated studies are needed. Antigen tests are interesting from a public health perspective, as they are rapid (approximately 15-20 minutes) compared to centralized amplification based testing e.g. RT-PCR, but previous antigen tests e.g. for Influenza and Respiratory Syncytial Virus have shown unacceptable low sensitivity when compared to nucleic acid based testing (NAT, e.g. RT-PCR) (Chartrand 2012, Bruning 2017, Merckx 2017). CE marked antigen tests are mostly validated for use with nasopharyngeal swabs. Unfortunately, nasopharyngeal swabbing is normally avoided in adults due to the discomfort for the patient leading to risk of non-compliance and are widely substituted by oropharyngeal swabbing. In the present protocol oropharyngeal

	swabs or less invasive testing e.g. nasal swabs will be used to limit the discomfort for the participating individuals and to reflect the real-life testing approach in adults. An alternative test strategy with saliva swabs with RT-PCR testing will be included as part of the study.
Objectives	To evaluate the analytical and clinical sensitivity and specificity of antigen tests performed as oropharyngeal swabs, outer nasal swabs, saliva swabs, self-test or breath tests for SARS-CoV-2 towards standard RT-PCR testing
Trial design	Prospective accuracy observational study combined with retrospective analytical sensitivity and specificity study.

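### Throat RT-PCR as the sole reference supports agreement with throat RT-PCR, but not a ranking of antigen tests taken from different sites

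*Protocol*

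**What the plan says.** The Objectives row of the Protocol lists the index tests as oropharyngeal "swabs, outer nasal swabs, saliva swabs, self-test or breath tests for SARS-CoV-2 towards" standard RT-PCR.

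Under Statistical methods the rule is general: "Prospective arm: Performance of each antigen test will be reported as sensitivity", along with specificity and predictive values. The reference follows: "compared to oropharyngeal swabs evaluated by RT-PCR. Clinical performance of" (the last words begin the next sentence). No other reference for antigen tests is given in this arm.

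The Interventions row describes throat sampling as three swabs at a time: "procedure. The three swabs are held together and rotated at both tonsils and at the" back of the throat. Other sites are sampled separately, with material "collected for additional antigen and RT-PCR testing". For retested positives, one throat swab goes to the central laboratory, together with other-site samples where relevant.

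The only stated use of other-site RT-PCR is a secondary outcome: "Agreement between oropharyngeal swabs and tests from other anatomical test" locations, by RT-PCR.

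Comparisons between tests are covered by one sentence: "Comparison of sensitivity and specificity between antigen test will be done using" McNemar's test. It names no pairs and sets no limit by sampling site. The sample size is 200 RT-PCR positives and 200 RT-PCR negatives per antigen test.

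**The concern.** A throat antigen swab and a throat RT-PCR swab taken in one pass share site, moment and technique. If the pass picks up no virus, both are negative and the pair counts as agreement. A nasal or saliva sample has its own chance of success or failure. If it fails while the throat sample succeeds, it is a false negative. If it succeeds while the throat sample fails, its correct positive falls outside the sensitivity denominator and counts as a false positive.

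The study sets out to learn whether less invasive sampling can serve in adults. If a throat-referenced McNemar result between a throat test and a nasal or saliva test is read as a difference in accuracy, part or all of it may be shared sampling. The error has one direction, so more participants make it more significant, not smaller.

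**Working it through.** **1. Inputs.** From the Protocol: throat RT-PCR as reference, McNemar between tests, 200 RT-PCR positives per test. The Protocol gives no derivation of the 200 and no expected sensitivity, alpha, power or between-site concordance, so there is no figure of its own to reproduce. Assumptions made here: two-sided 5% level, and the same 200 throat-positive people take both tests.

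**2. Direction, without assuming independence.** Take infected people and two tests with the same overall detection, P(throat Ag+) = P(other Ag+). Suppose every true-positive antigen result comes with a positive RT-PCR at its own site.
- Throat test: P(throat Ag+ | throat PCR+) = P(throat Ag+) / P(throat PCR+).
- Other-site test: P(other Ag+ | throat PCR+) ≤ P(other Ag+) / P(throat PCR+), the same value.

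Equality holds only if the other-site test detects nobody who is throat RT-PCR negative. The other-site test is therefore never favoured.

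**3. Size, under assumptions.** Let s = 0.75 be detection given an adequate sample and a the adequacy at each site, independent between sites. RT-PCR is positive when the sample is adequate. Among throat RT-PCR positives:
- throat sensitivity = s; other-site sensitivity = s·a
- share positive on throat only: b = s(1 − s·a)
- share positive on other site only: d = s·a(1 − s)

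At a = 0.80: b = 0.75 × (1 − 0.60) = 0.30 and d = 0.60 × 0.25 = 0.15, so 60 against 30 discordant pairs are expected in 200. Rejection rates were simulated.

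| Adequacy a | Throat | Other site | McNemar p < 0.05 | With continuity correction |
|---|---|---|---|---|
| 0.80 | 75% | 60% | 90% | 87% |
| 0.85 | 75% | 64% | 69% | 64% |
| 0.90 | 75% | 68% | 38% | 33% |
| 0.95 | 75% | 71% | 14% | 11% |
| 1.00 | 75% | 75% | 5% | 4% |

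**4. Sensitivity to the assumptions.** With s = 0.80 and other-site RT-PCR positive in 80%, 85%, 90% or 95% of throat positives, the rates are 95%, 79%, 47% and 16%. Over s from 0.6 to 0.9 and the same concordance range, the artificial gap runs from 3 points (0.6 × 0.05) to 18 points (0.9 × 0.20). If adequacy is correlated between sites, concordance rises and the gap shrinks. If antigen results also agree whenever both sites are positive, the gap stays the same but is detected more often (96% or more at s = 0.80 and concordance of 95% or less).

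**5. Alternative reference.** With positive at either of the two sites as reference, every true-positive antigen result from either site lies inside the reference-positive group. Both sensitivities then equal P(Ag+) / P(either PCR+), so tests with equal detection score equally. In the model of step 3 both equal s·a / (1 − (1 − a)²) = 0.75 / (2 − a): 62.5%, 65.2%, 68.2% and 71.4% at a = 0.80, 0.85, 0.90 and 0.95. The throat test falls by 12.5, 9.8, 6.8 and 3.6 points from 75%.

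**The case against.** The strongest reply is that the question is agreement with the standard test. The title and Objectives say so, and the Background states that throat swabbing is what is widely used in adults. For that question, a nasal test that misses throat RT-PCR positives does agree less, and one common reference is a recognised choice. This stands. A reader might infer that the throat reference is wrong for the study, or that non-throat results against it are invalid; the documents do not support that. What it does not cover is a between-site comparison read as a difference in test accuracy.

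Second, the McNemar sentence names no pairs and directly follows the retrospective-arm text, so use across sites comes from its general wording, not from an explicit plan. The selection of pairs could sit in an analysis plan not shown here. This is fair, and is a reason to clarify. The wording as it stands permits the comparison.

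Third, the secondary outcome on RT-PCR agreement between sites will make the discordance visible. It will, but it does not correct the antigen estimates or the comparisons.

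Fourth, the size rests on assumed adequacy and independence. This stands: at 98% adequacy the rejection rate is about 6%, near nominal. A reader might infer that less invasive tests will in fact be found inferior; the Protocol gives no concordance figure from which to say so.

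Fifth, that the jointly held swabs supply both RT-PCR and antigen tests is the natural reading of Interventions, not stated word for word. With three swabs per pass and a range of antigen tests, not every throat antigen test need share the reference pass. Even so, the throat test still shares the anatomical site.

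**Conclusion.** The point holds for the prospective arm, limited to comparisons between a throat test and a test from another site. Throat RT-PCR is a sound reference for agreement with standard testing and should stay primary. It cannot support a ranking across sites: under the conditions in step 2, an equally good other-site test looks equal or worse, never better.

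Under assumed 75% detection and independent adequacy of 80% to 95%, the spurious gap is about 15 to 4 points, and McNemar with 200 paired positives flags it in about 90% to 14% of studies. The effect vanishes with perfect concordance between sites.

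Two wider readings are not supported. The retrospective arm is unaffected, because its antigen tests and RT-PCR use the same stored material. Nor can the point be stated in the same way for breath tests, for which no RT-PCR at the site is clearly described, or for self-tests, whose sampling site is not given. For those, the only safe statement is agreement with throat RT-PCR.

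**What to change.** In Statistical methods, for the prospective arm:

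1. Keep throat RT-PCR as the primary reference, and state that results against it measure agreement with throat RT-PCR.
2. For each comparison of a throat test with a nasal or saliva test, add an analysis in participants with RT-PCR at both sites. Fix the reference for that pair as positive at either of the two sites. Report sensitivity against each test's own-site RT-PCR as a check; these have different denominators, so give them side by side rather than by McNemar.
3. State that a McNemar difference between sites against throat RT-PCR alone will not be read as a difference in test accuracy.
4. Where a site has no RT-PCR (breath tests, self-tests with no stated site), limit conclusions to agreement with throat RT-PCR.

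No new type of sample is needed, but the change has a price. Other-site RT-PCR is taken only where relevant, so the added analysis uses a smaller subset of unknown size. In it, throat-test sensitivity would be about 4 to 12.5 points lower under the assumptions above, and should not be confused with the primary figure. Fixing the reference pair by pair means that results are not interchangeable across pairs. Some tilt may remain, because retested cases entered through an earlier positive RT-PCR, which may itself have favoured people with a positive throat swab.
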